1 INTRODUCTION

STABILIZE-CKD is a Phase 3, International, Randomised, Double-blind, Placebo controlled Study to Evaluate the Effect of Sodium Zirconium Cyclosilicate on Chronic Kidney Disease (CKD) Progression in Participants with CKD and Hyperkalaemia or at Risk of Hyperkalaemia. For details on study background and rationale, please refer to the Clinical study protocol for STABILIZE-CKD (CSP, D9488C00001, Version 2.0 (16Jun2022)).

This Statistical Analysis Plan (SAP) provides further details of the summaries and analyses to be performed to report the findings in the CSR and should be read in conjunction with the STABILIZE-CKD Clinical Study Protocol (CSP).

2 CHANGES TO PROTOCOL PLANNED ANALYSES

No changes were made to the analyses as described in the CSP.

3 DATA ANALYSIS CONSIDERATIONS

3.1 Timing of Analyses

Only one set of analyses will be performed to write the CSR. These will be performed at the end of the study after the data base is locked and all data is available.

3.2 Analysis Populations

The study consists of five analysis populations, namely:

Populations for Analysis

| Population/analysis set | Description |
|---|--|
| Enrolled | All participants who sign the ICF. |
| Safety analysis set, initiation phase (SAS-IP) | All participants receiving at least one dose of Initiation SZC. |
| Safety analysis set, run-in phase (SAS-RIP) | All participants receiving at least one dose of Run-in SZC, regardless within or without the run-in phase. |
| Safety analysis set, maintenance phase (SAS-MP) | All randomized participants receiving at least one dose of Maintenance SZC or Maintenance-phase placebo, regardless within or without the maintenance phase. |
| Full analysis set (FAS) | All randomised participants. |

3.3 General Considerations

For the purpose of describing the data, summary statistics illustrating the empirical distribution of the variables will be tabulated for most of the collected measurements.

Continuous variables will be summarised using the following descriptive statistics: n (the number of patients included in the analysis), mean, median, standard deviation, minimum, maximum and quartiles where appropriate. Categorical variables will be summarised using number and percentage of observations in each category, with the denominator for the percentages depending on the type and purpose of analyses (e.g., the number of subjects in an analysis set will be used for the tabulations of the baseline characteristics, but number of subjects with available data at a visit will be used for summary statistics by visit tabulations).

In addition, time to event variables will be summarised using Kaplan-Meier estimators of the CDF function. For a selection of continuous variables, in the absence of censoring, the whole eCDF function, rather than a number of different kinds of summary statistics, might be plotted.

3.3.1 General Study Level Definitions

3.3.1.1 Baseline

Different baselines will be defined for the initiation, run-in and the maintenance phases. For each of these phases, the baseline will be defined as the value obtained on the first day of the phase, or, if such a measurement is missing, within a certain number of days prior to the first day of the phase, namely: within 14 days for the Initiation-Phase, within 1 day for the Run-In Phase and within 5 days for the Maintenance Phase. See Section 3.3.1.3 for the definition of the different phases of the study.

3.3.1.2 Imputation of Missing Dates

No imputation will be done for missing or partial missing dates, except for start and end date for concomitant medication, which will be imputed as indicated below. For the purpose of this imputation, "first dose" refers to the (scheduled) beginning of SZC administration in the initiation phase.

- Missing start day - impute as the 1st of the month unless the month is the same as month of first dose of study drug, then impute start day as date of first dose of study drug.
- Missing start day and month – impute 1st of January unless year is the same as for first dose date, then impute first dose date. Ensure that the start date is prior to the end date of the concomitant medication.

- Start day completely missing - impute first dose date unless the end date suggests it could have started prior to this in which case impute the 1st of January of the same year as the end date of the concomitant medication.

When imputing a start date ensure that the new imputed date is sensible, i.e., is prior to the end date of the medication.

- Missing end day - impute the last day of the month unless month is same as the date of contact with the patient, then impute the date of last contact.
- Missing end day and month – impute 31st of December unless year is the same as the date of last contact, then impute the date of last contact.
- End date completely missing - if the ongoing flag is missing, then assume that the medication is still being taken, i.e., do not impute a date. If the medication has stopped and start date is prior to first dose date, then impute the 1st dose date. If it started on or after first dose date, then impute to be the date of last contact.

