4.1.8 Concomitant Medications

4.1.8.1 Definitions and Derivations

Concomitant medications, including medications taken during the screening period, will be collected in the eCRF and classified by ATC classification and generic term.

Baseline medications for a particular phase are defined as medications with a start date no later than the beginning of the phase in question, and a stop date after the beginning of the phase (or ongoing at the end of study).

Concomitant medications for a particular phase are defined as medications which a patient takes during that phase. Explicitly, it is medications with a start date earlier than the end of the specific phase and a stop date during or after the same phase (or ongoing at the end of study). Missing start and stop dates will be handled as set out in Section 3.3.1.2.

A rescue medication is defined as a medication used in connection to the adverse event of severe hyperkalaemia requiring rescue as determined by the investigator.

Two types of medications are considered to be disallowed in the study:

- **A potassium binder is disallowed** if it is not a short term (≤ 2 days) rescue medication. Potassium binders are defined by the following ATC codes / ingredients:

Table 1: Disallowed potassium binders

| ATC code | Ingredients |
|----------|-------------------------------|
| V03AE | SODIUM POLYSTYRENE SULFONATE |
| V03AE | CALCIUM POLYSTYRENE SULFONATE |
| V03AE | PATIROMER |
| V03AE | PATIROMER CALCIUM |
| V03AE | PATIROMER SORBITEX CALCIUM |

- **RAASi medication is disallowed** if it is taken concomitantly with Valsartan or Lisinopril, after the initiation phase, as specified by the CSP.

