- Treatment (SZC vs Placebo).
- Geographic region.
- Hyperkalaemia at the beginning of the initiation phase (yes/no), as indicated by the strata applied at randomisation.
- Use of SGLT2i/Finerenone at randomisation (yes/no), as indicated by the concomitant-medications collection.
- Age.

Further covariates may be added as appropriate, and these will be specified in the descriptions below.

Table 2: Overview of the main and the supplementary analyses

|

| Statistical category | Endpoint | Intercurrent event strategy | Population level summary | Details in section |
|--|---|--|--|--------------------|
| Primary | | | | |
| Primary objective #1: To determine if treatment with S2C, as adjunct to ACEi/ARB therapy (lisinopril or valsartan), is superior to placebo in slowing CKD progression, assessed as the reduction in participant's expected eGFR decline over time | | | | |
| Main | Total slope: eGFR measurements starting at randomisation (up to visit 17/week 69) | Main strategy | Difference in mean total eGFR slopes | 4.2.1.1 |
| | Chronic slope: eGFR measurements, starting at 12 weeks after randomisation (up to visit 17/week 69) | Main strategy | Difference in mean chronic eGFR slopes | 4.2.1.1 |
| Supplementary | Total slope: eGFR measurements starting at randomisation (up to visit 17/week 69) | Hypothetical strategy wrt initiation of long-term potassium lowering treatment and initiation of potentially eGFR altering treatment | Difference in mean total eGFR slopes | 4.2.1.2 |
| | Chronic slope: eGFR measurements, starting at 12 weeks after randomisation (up to visit 17/week 69) | Hypothetical strategy wrt initiation of long-term potassium lowering treatment and initiation of potentially eGFR altering treatment | Difference in mean chronic eGFR slopes | 4.2.1.2 |

| Statistical category | Endpoint | Intercurrent event strategy | Population level summary | Details in section |
|----------------------|----------|-----------------------------|--------------------------|--------------------|
| Secondary | | | | |
| | | | | |

Secondary objective #1: To determine if treatment with SZC, as adjunct to ACEi/ARB therapy (lisinopril or valsartan), is superior to placebo in reducing the incidence of the composite of kidney failure outcomes comprising: sustained $\geq 40\%$ decline in eGFR, onset of ESKD, and death from kidney failure

| Statistical category | Endpoint | Intercurrent event strategy | Population level summary | Details in section |

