4.2.1.3 Supplementary analyses

The following supplementary analyses of the primary endpoint will be performed:

Impact of introduction of concomitant medications

Two supplementary analyses (one for each of the primary endpoints) will be performed for the evaluation of the potential impact that the intercurrent events of an introduction of a long-term treatment that affects either potassium, or eGFR profile, will have on the treatment effect of SZC.

For the analyses, the eGFR measurements that are obtained after the introduction of long-term potassium-lowering concomitant treatment or concomitant medication that has direct effect on CKD progression will be removed. That is, the time point at which such treatments are introduced will be regarded as a point of censoring.

The main analysis of the primary endpoint will then be replicated using the resulting data set.

Again, due to the early close-down of the study and the ensuing unavailability of late eGFR measurements, only measurements taken up to and including visit 17 (week 69) will be included in the mixed-effects model.

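### SAP 3.3.1.2 never checks imputed concomitant-medication dates against randomisation, so some incomplete dates misstate SGLT2 inhibitor/finerenone use at randomisation, a supplementary censoring date and baseline medication

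*SAP*

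**What the plan says.** SAP 3.3.1.2 uses a single anchor. First dose "refers to the (scheduled) beginning of SZC administration in the initiation phase". The start rules are:

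- Day missing: "impute as the 1st of the month unless the month is the same as month of first dose of study drug", in which case the first dose date is used.
- Day and month missing: "impute 1st of January unless year is the same as for first dose date, then impute first dose date".
- Completely missing: "impute first dose date unless the end date suggests it could have started prior to this".

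The only check on an imputed start is that it comes before the end of the medication. For a completely missing end date on a stopped drug: "If the medication has stopped and start date is prior to first dose date, then impute the 1st dose date". If the drug began on or after first dose, the end becomes the date of last contact. Partial end dates go to the end of the month or year, or to last contact.

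SAP 4.1.8.1 sends missing dates to these rules. It defines baseline medication for a phase as one that started no later than the beginning of the phase "and a stop date after the beginning of the phase" (or is ongoing). SAP 3.3.1.3 starts the initiation phase on the day of first dose and the maintenance phase on the day of randomisation.

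Two efficacy uses follow. SAP 4.2 lists as a covariate "Use of SGLT2i/Finerenone at randomisation (yes/no), as indicated by the concomitant-medications collection", and 4.2.1.4 uses the same factor as a subgroup. In the 4.2.1.3 analysis, "the time point at which such treatments are introduced will be regarded as a point of censoring".

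**The concern.** The anchor suits questions about study entry. The quantities that matter for efficacy are defined at or after randomisation, and no rule refers to that date or to the phase being classified. A drug begun during follow-up can therefore be counted as use at randomisation, which puts post-randomisation information into a covariate meant to be fixed at baseline. The same imputed date would set the censoring point in the supplementary analysis that Table 2 describes as a hypothetical strategy. In the other direction, a drug in use at the start of a phase can disappear from that phase's baseline.

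**Working it through.** The plan states no figure on this point, so there is none to reproduce. The rules were applied to worked dates, and the year-only rule was then sized under stated assumptions. A completely missing start is taken to go to first dose unless a known end date precedes first dose.

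**Worked dates.** First dose 10 Mar 2022, run-in from 13 Mar 2022, randomisation 8 Jun 2022 (90 days after first dose).

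| True history | What is missing | Imputed | Result |
|---|---|---|---|
| Start 15 Sep 2022 | Day and month | Start 10 Mar 2022 | Wrongly in use at randomisation |
| Start 15 Feb 2023 | Whole start date | Start 10 Mar 2022 | Wrongly in use at randomisation |
| Start 15 Feb 2023 | Day and month | Start 1 Jan 2023 | Correctly after randomisation, but early |
| Start 15 Sep 2022 | Day | Start 1 Sep 2022 | Correctly after randomisation |
| Started 2020, stopped 1 Sep 2022 | Whole end date | Stop 10 Mar 2022 | Baseline for no phase; truth is all three |
| Started 2020, stopped Sep 2022 | Day of end date | Stop 30 Sep 2022 | Correctly kept |
| Started 11 Mar 2022, stopped before randomisation | Whole end date | Stop at last contact | Wrongly kept at randomisation |

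The fifth row fails because the imputed stop equals the first day of the initiation phase, while 4.1.8.1 needs a stop later than that day.

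The year-only error also occurs when the first dose falls in the previous year. With first dose 1 Nov 2022 and randomisation 30 Jan 2023, a start on 15 Sep 2023 recorded as 2023 becomes 1 Jan 2023, which precedes randomisation.

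**Share of year-only starts dated on or before randomisation.** Assumptions, none from the documents except the follow-up length and the approximate run-in length: first dose uniform over a 365-day year, randomisation 93 days later, true start uniform over the 69 × 7 = 483 days after randomisation.

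- First dose and randomisation in the same year (first dose in the first 365 − 93 = 272 days), start also in that year: 272² / (2 × 483 × 365) = 73,984 / 352,590 = 21.0%.
- Randomisation in the next year (the other 93 days), start in the randomisation year: (365 × 93 − 93²/2) / (483 × 365) = 29,620.5 / 176,295 = 16.8%.
- Total 37.8%. Simulation of 400,000 records gave 37.6%.
- Over 104 weeks (728 days): 37.8% × 483/728 = 25.1%; simulation 25.0%.

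Year-only starts that stay after randomisation are dated a mean of about 145 days early (simulation, 69 weeks). For completely missing starts the share is 100%, but that only restates the rule.

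**Censoring.** SAP 4.2.1.3 removes eGFR obtained after introduction of the drug. If the imputed introduction precedes randomisation, a literal reading removes all post-randomisation eGFR for that participant. A reading that treats the drug as baseline use removes none. The SAP does not choose. If the imputed date is after randomisation but too early, eGFR measured before the true start is deleted.

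**The case against.** Much can be said against a broad version of this point, and most of it stands.

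- **Rarity.** Protocol 6.5 requires start and end dates for every medication, so a year-only or blank start for a drug begun during follow-up should be unusual.
- **Inferred link.** SAP 4.2 names the medication collection as the source of the covariate but cites neither the 4.1.8.1 definition nor 3.3.1.2. The route into the model is the natural reading, since no other date rule is given, but it is not stated.
- **Main analysis.** The main strategy is treatment policy, with data excluded only after onset of ESKD. Drug starts do not remove data from the co-primary models. A reader might infer that the slope comparison is biased. The documents do not support that: the only route is misclassification of one adjustment covariate in an unknown number of participants.
- **Stopped drugs.** A reader might infer that stopped drugs generally drop out of every baseline. They do not. The error needs a stopped flag, a start before first dose, a completely missing end date and a true stop after the phase began.
- **ACEi/ARB.** A reader might expect a non-study ACEi/ARB to be missing wrongly from the maintenance baseline. Protocol 6.6.2 switches these drugs on the first run-in day and Table 6 bars them alongside the study drug after initiation, so absence at randomisation is normally right. Only the initiation baseline is wrong, since Protocol 4.1.2 keeps ACEi/ARB unchanged during that phase.
- **SGLT2 inhibitors.** Inclusion criterion 8 concerns stability before screening. It does not show that a drug stopped later was still in use at randomisation.
- **Month-only dates.** Those in the randomisation month can also be misplaced (about 3% under the same assumptions), but through first-of-month imputation, not the first-dose anchor.
- **Potassium binders.** A one-day rescue binder dated only by month would appear to exceed two days. That is not an efficacy problem: SAP 4.1.8.2 only summarises disallowed drugs, and 4.2.1.3 concerns long-term treatment without using the two-day rule.

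None of this answers the narrower point that the stated rule, followed as written, gives a wrong classification in identifiable cases.

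**Conclusion.** The point holds in a limited form. For the start patterns identified above, an SGLT2 inhibitor or finerenone begun after randomisation is dated on or before it. If the covariate and subgroup use these dates, it is misclassified as use at randomisation, and its censoring point in 4.2.1.3 is wrong or undefined. A drug begun before first dose, flagged stopped and lacking any end date, is baseline for no phase, even if it was in use at the start of initiation (ACEi/ARB) or at randomisation (SGLT2 inhibitor/finerenone).

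The 38% and 25% figures are conditional on a year-only start and on the assumed uniform timing. The overall effect cannot be sized, because the documents give no frequency of incomplete dates. This is a cheap correction to one covariate, one subgroup, one supplementary analysis and the baseline-medication tables. It does not call the co-primary result into question.

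**What to change.** Add two rules to SAP 3.3.1.2 for uses tied to randomisation or to a phase baseline.

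1. **Starts.** When an incomplete SGLT2 inhibitor or finerenone start is compatible with dates both before and after randomisation, take use at randomisation from the recorded stratification value where there is one. It may be absent for participants randomised before Amendment 1 added the factor. Otherwise use the medications recorded by Visit 6b. If the drug was not in use then, impute the start no earlier than the day after randomisation. Use the same date for censoring in 4.2.1.3.
2. **Stops.** For a stopped drug with no end date, replace the first-dose stop with a date no earlier than the latest evidence of use: for example, a stratification value showing use at randomisation, or, for a non-study ACEi/ARB, the switch at run-in entry.

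State in 4.2 that the covariate and subgroup follow these rules. The fix should not depend on visit-stamped medication records during maintenance, which the documents do not confirm. A recorded stratum can itself be wrong (SAP 3.3.5 lists incorrect stratification as an important deviation), so it should decide only where the dates do not.

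The cost is a few lines of wording and slightly more programming. Some uncertainty in the imputed dates will remain.

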3.3.1.3 Study Periods

The study consists of five distinct study periods, namely: Screening phase, Initiation phase, Run-In phase, Maintenance phase and Follow-Up phase. Participants will transfer directly between study periods in the order given.

The five phases are delimited in time like this:

Screening phase

- *First day*: the day of the date of signature on the signed informed-consent form (ICF).
- *Last day* (if participant not going into Intervention period/Initiation phase): the day of last contact.
- *Last day* (if participant going into Intervention period/Initiation phase): the day before first Initiation-phase S2C-dose.

Note: If there is no signed ICF, then there is no Screening phase, and no other phases either.

Initiation phase

- *First day*: the day of first Initiation-phase S2C-dose.
- *Last day* (if not going into Run-in phase): the day of last Initiation-phase S2C-dose.
- *Last day* (if going into Run-in phase): the day before the first day of the Run-in phase (see below).

Run-in phase

- *First day*: the day of first Run-in SZC dose, or the day of first Run-in (IP) RAASI-dose, whichever comes first, however no earlier than the day after last Initiation-phase SZC-dose.
A consequence of this is that the Run-in phase always has its first day on the day after last Initiation-SZC dose, *at the earliest*; if any Run-in IP (SZC, lisinopril, valsartan, irbesartan), would be initiated before, or on the same day as, the last Initiation SZC dose, then the Run-in phase will start on the day after the day of last Initiation-SZC dose. This means that any Initiation-SZC dosing takes precedence over any Run-in IP dosing when it comes to separating the Initiation phase and the Run-in phase, in favour of the Initiation phase. If – on the other hand – both Run-in SZC and Run-in RAASI would start on a day (potentially different days for Run-SZC and Run-in RAASI) *after* the day of last Initiation SZC then the Run-in phase will have its first day on the day of the earliest initiation of any of the two Run-in IP types (SZC or RAASI). This means that any time “gap” between Initiation SZC and Run-in IP will be assigned to the Initiation phase.
- *Last day* (if not going into Maintenance phase): the day of last Run-in SZC-dose, or the day of last Run-in (IP) RAASI-dose, whichever comes last.
- *Last day* (if going into Maintenance phase): the day before the day of randomisation.

Maintenance phase

- *First day*: the day of randomisation.
- *Last day*: the day of last contact.

Note: No Follow-up phase will follow the Maintenance phase.

Follow-up phase

- *First day*: The day after last day of the immediately preceding phase (Initiation phase or Run-in phase; no Follow-up phase will follow the Maintenance phase and the Screening phase; see above). However, if the day of last contact would occur in a preceding phase, then there will not be any Follow-up phase.
- *Last day*: The day of last contact.

Note 1: A Follow-up phase can only occur following the end of the Initiation phase or following the end of the Run-in phase. No Follow-up phase will occur after the Maintenance phase.

Note 2: There will not be any Follow-up phase if the day of last contact would occur in a preceding phase.

For the purpose of presentation of **safety analyses**, the follow up phase will generally be combined with the phase that directly precedes it.

For the purpose of presentation of **patient disposition**, the study periods as provided by the investigator (such an option exists in the CRF for disposition events in particular) will be used.

